15.8 Secondary Efficacy Analysis

The total score for MFM and the subtotal for each of the three dimensions (Standing and transfer, Axial and proximal motor function, and Distal motor function) will be standardized by the possible maximum for both MFM 20 and MFM 32. The CFB for these standardized scores will be analyzed using the standard analysis for a 2-by-2 crossover design for MFM 20 and MFM 32 separately and pooled, with the latter being the secondary and the separate analyses being supportive. The total scores, subtotals for each dimension, and the corresponding standardized scores will be summarized by treatment and period for MFM 20 and MFM 32 separately and standardized scores will be summarized by treatment and period for MFM 20 and MFM 32 pooled. P-values <0.05 will be considered statistically significant.

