9 STUDY OBJECTIVES

9.1 Primary Objectives

The primary objectives of the study are:

- To characterize the overall safety and tolerability of amifampridine phosphate compared with placebo in patients with CMS; and
- To assess the clinical efficacy of amifampridine phosphate compared with placebo in patients with CMS, based on improvement in subject global impression (SGI) and motor function measure (MFM 20 or 32) scores.

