15.7 Primary Efficacy Analysis

The analysis of CFB for SGI is the primary efficacy analysis and will be performed using the standard analysis for a 2-by-2 crossover design. Summary statistics for SGI and CFB for SGI will be presented by treatment and period. P-values <0.05 will be considered statistically significant.

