1.1 Design and Treatment

This randomized (1:1), double-blind, placebo-controlled, outpatient two-period, two-treatment crossover study is designed to evaluate the efficacy and safety of amifampridine phosphate in patients diagnosed with certain genetic subtypes of CMS and demonstrated open label (amifampridine phosphate) or history of sustained amifampridine benefit from treatment. The primary objectives of this study are to:

- Characterize the overall safety and tolerability of amifampridine phosphate compared with placebo in individuals with CMS; and,
- Assess the clinical efficacy of amifampridine phosphate compared with placebo in individuals with CMS, based on change in Subject Global Impression (SGI) and Motor Function Measure (MFM 20 or 32) scores.

CMS-001 is a randomized double-blind, placebo controlled, two-period two-treatment crossover study designed to evaluate the efficacy and safety of amifampridine phosphate in children (2-16 years of age) and adults (17 years of age or more) diagnosed with CMS. Patients were randomized (1:1) to one of two sequences:

PA: Placebo – Amifampridine, or
AP: Amifampridine – Placebo.

The study was planned to include up to 23 male and female subjects. The planned duration for each patient is approximately 56 days, excluding the screening period. The screening period may last up to 14 days.

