2.0 Data Analysis Considerations

2.1 Types of Analyses

The term summary statistics for quantitative data refers to the following list of statistics unless otherwise specified: n (number of non-missing observations), mean, standard deviation, minimum, median, and maximum. Categorical variables will be summarized with frequency counts and percentage of the relevant group. Summary statistics will be summarized by treatment sequence and study period. Unless otherwise stated, all hypotheses will be tested at a two-sided $\alpha = 0.05$ significance level

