4.1.2 Description of Secondary Efficacy Variables

The following variables will be secondary measures of efficacy:

- Motor Function Measure 20 (MFM-20, for Pediatric Subjects under 7 years) or Motor Function Measure 32 (MFM-32, for all other subjects). MFM-20 or MFM-32 Scores, depending on age, will be calculated as Totals for all items. MFM-20 and MFM-32 dimension scores are totals for item group D1 (Standing and Transfer), item group D2 (Axial and Proximal Motor Function), and item group D3 (Distal Motor Function). Additionally, these Motor Function Measure outcomes are also expressed as a percentage of the respective maximum possible total for all items and the three dimension groups, for both the MFM 20 and MFM 32. The percentages "normalize" the response between MFM 20 and MFM 32 so that

outcomes from these two groups of test subjects can be pooled for analysis across age groups;

- Clinical Global Impression-Severity;
- Clinical Global Impression-Improvement;
- Stimulated Single Fiber Electromyogram: mean jitter, median jitter, and percent block (this optional test is described in the protocol but not conducted at all trial sites);
- Slurp Test: Time (seconds) to make slurp sound (this optional test is described in the protocol but not conducted at all trial sites).

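### MFM results may be called significant at p<0.05 whether or not SGI succeeds, and the MFM total is not ranked above its three dimensions

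*Protocol*

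**What the plan says.** **Primary variable.** Protocol 15.7 states: "The analysis of CFB for SGI is the primary efficacy analysis". It sets significance at p<0.05. SAP 4.1.1 lists SGI as the only primary efficacy variable.

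**MFM.** Protocol 15.8 covers "The total score for MFM and the subtotal for each of the three dimensions", each standardized to its possible maximum, and repeats the rule: "P-values <0.05 will be considered statistically significant". The only ranking inside MFM is pooled against separate forms, "with the latter being the secondary and the separate analyses being supportive". SAP 4.1.2 introduces the list that contains MFM with "The following variables will be secondary measures of efficacy".

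**Objective.** Protocol 9.1 assesses efficacy "based on improvement in subject global impression (SGI) and motor function measure (MFM 20 or 32) scores". SAP 1.1 has the same pairing, "based on change in Subject Global Impression (SGI) and Motor Function Measure (MFM 20 or 32) scores". Neither says whether success needs both measures or one of them.

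**Error rate.** SAP 2.1 reads "Unless otherwise stated, all hypotheses will be tested at a two-sided" level of 0.05. I found no testing order, gate, alpha split or adjustment in Protocol section 15 or SAP sections 2 and 4.

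**The concern.** The labels primary and secondary rank the endpoints, but they do not make one test depend on another. Read literally, Protocol 15.8 allows an MFM result to be declared significant after SGI has failed. Because the total is not placed ahead of the dimensions, any of four pooled scores could carry that statement.

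This matters more than usual because MFM stands beside SGI in the primary efficacy objective. A positive dimension score could be presented as support for that objective with no stated error rate behind it.

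**Working it through.** **Inputs.** Two-sided 0.05 per test (Protocol 15.7 and 15.8; SAP 2.1). Five tests: SGI, pooled MFM total, D1, D2 and D3 (Protocol 15.7 and 15.8). Maximum scores of 39, 36 and 21, which sum to 96, for MFM 32, and 24, 24 and 12, which sum to 60, for MFM 20 (SAP Table 4.2-2). Effect size 0.5, defined as the difference over the SD of the difference, with 23 per sequence (SAP 1.3). The documents give no correlations between scores, so those below are assumptions.

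**1. The plan's own figure.** N = 46, non-centrality 0.5 × √46 = 3.39, 44 df, two-sided 0.05. Power is 91.2%; with 44 patients it is 89.97%. So 23 per sequence for 90% power is reproduced. The calculation serves SGI alone at the full 0.05 and makes no provision for MFM.

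**2. Independent-test reference.** The chance of at least one false positive among k tests is 1 − 0.95^k.
- k = 2: 9.75%
- k = 4: 18.5%
- k = 5: 22.6%

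The last two are upper references only, because the MFM total is the sum of its dimensions and cannot be independent of them.

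**3. Total built from its dimensions.** I simulated null z-tests from a multivariate normal distribution (at least 1,000,000 draws per row). The three dimensions share correlation r_d, and SGI has correlation r_s with each. The total is (39·D1 + 36·D2 + 21·D3)/96, rescaled to unit variance. This takes the MFM 32 weights and equal variance for the three dimension percentages. A test is positive if |z| > 1.96.

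| r_d | r_s | Any of 5 | Any of 4 MFM | SGI or MFM total |
|---|---|---|---|---|
| 0 | 0 | 20.2% | 16.0% | 9.8% |
| 0.5 | 0 | 17.4% | 13.0% | 9.8% |
| 0.5 | 0.5 | 15.9% | 12.9% | 8.8% |
| 0.9 | 0.5 | 12.0% | 8.3% | 9.0% |
| 0.8 | 0.8 | 11.4% | 9.9% | 7.4% |

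The ranges are about 11-20%, 8-16% and 7-10%. As all correlations approach 1, every column falls towards 5%.

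**4. If the objective requires both.** A false declaration then needs a false positive on at least one measure that has no effect, so its chance is at most 5%. That pair has no inflation; the cost is power. If MFM also had effect size 0.5, joint power with 46 patients would lie between 0.912² = 83% (independent) and 91% (fully correlated).

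**5. Effect of a fixed sequence.** If SGI has no effect, any false claim must first pass the SGI test, so the chance is at most 5%. If SGI works and MFM total does not, the chance of a false MFM claim is at most 5%. SGI power stays at 91.2%. Bonferroni over the five tests (0.01 each) would cut it to 75.4%. With 23 patients in total, the enrolment stated in Protocol 10.1, the figures are 62.8% and 35.7%.

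**6. Tests within each endpoint.** SAP 4.2.1 and 4.2.2 give SGI and MFM each a Period 1 Mann-Whitney-Wilcoxon test, a crossover Mann-Whitney-Wilcoxon test and a mixed model. Neither section says which one decides. The percentages above assume one test per score.

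**The case against.** The strongest reply is that the primary test is sound. SGI is the sole primary variable, the sample size is built on it, and testing secondary endpoints does not raise its error. This stands. A reader might infer from the shared objective that the trial's 5% error rate is lost. The documents do not support that: no passage treats an MFM result as success in place of SGI.

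The objective also joins SGI and MFM with *and*. If both are needed, the pair is not inflated. Protocol 9.1 puts every study objective, safety included, under the primary heading, so it is weak evidence that MFM shares primary status. This also stands, but neither document settles the reading, and the dimension scores stay unranked either way.

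Some ranking does exist. The separate MFM 20 and MFM 32 analyses are supportive, SAP 4.2.2 presents the item analyses as a check on the suitability of MFM, and SFEMG and the slurp test have no formal inference. That narrows the gap to two places: no gate from SGI, and no order between the total and D1-D3.

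Finally, a simpler model with one common correlation for all five tests gives 18% at 0.5 and 13% at 0.8. These are too high, because they ignore that the total is made of its dimensions. The table gives 15.9% and 11.4%.

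**Conclusion.** The gap is real and limited to MFM claims. Protocol 15.8 lets any of four pooled MFM scores be called significant regardless of SGI, at an overall error of about 8-16% across those four. Counting SGI as well, the chance of at least one false positive is about 11-20%. For SGI or MFM total it is about 7-10%, and that figure bears on the primary objective only if either measure would suffice. All three ranges rest on the assumed correlations and on one test per score.

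SGI's own 5% is intact provided a single deciding SGI test is named, which SAP 4.2.1 does not yet do. The point deserves correction before unblinding, but it does not undermine the primary analysis.

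**What to change.** In Protocol 15.7-15.8 and SAP 4.2, state a fixed sequence:

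1. SGI change from baseline, by one named crossover test, at two-sided 0.05.
2. Only if step 1 is significant, pooled MFM total percent, by the same named crossover test, at two-sided 0.05.

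Label everything else nominal or supportive and report it with estimates and intervals: the Period 1 tests, the other model for each endpoint, D1-D3, MFM 20 and MFM 32 separately, CGI, individual items and subgroups. Add a sentence to Protocol 9.1 and SAP 1.1 saying how SGI and MFM together serve the efficacy objective.

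The cost is wording only: no visits, patients or data collection change, and SGI keeps its full alpha and power. The downside is that no confirmatory MFM claim can be made if SGI fails. The change should be made before unblinding, the point by which Protocol 15.6 requires the SAP to be final.

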15.9 Changes in the Conduct of the Study

Any change in study conduct considered necessary by the investigator will be made only after consultation with Catalyst, who will then issue a formal protocol amendment to implement the change. The only exception is when an investigator considers that a patient's safety is compromised without immediate action. In these circumstances, immediate approval of the chairman of the IRB/IEC/REB must be sought, and the investigator should inform Catalyst and the full IRB/IEC/REB within 2 working days after the emergency occurs.

	CMS-001 Version Amendment 5	Page 70
---	--------------------------------	---------

16 COMPENSATION, INSURANCE, AND INDEMNITY

There will be no charge to study patients to be in this study. Catalyst will pay all costs of tests, procedures, and treatments that are part of this study (as included in the site budget). In addition, after IRB/IEC/REB approval, Catalyst may reimburse the cost of travel for study-related visits. Catalyst will not pay for any hospitalizations, tests, or treatments for medical problems of any sort, whether or not related to the study patient's disease that are not part of this study. Costs associated with hospitalizations, tests, and treatments should be billed and collected in the way that such costs are usually billed and collected.

The investigator should contact Catalyst immediately upon notification that a study patient has been injured by the IP or by procedures performed as part of the study. Any patient who experiences a study-related injury should be instructed by the investigator to seek medical treatment at a pre-specified medical institution if possible, or at the closest medical treatment facility if necessary. The patient should be given the name of a person to contact to seek further information about, and assistance with, treatment for study-related injuries. The treating physician should bill the patient's health insurance company or other third party payer for the cost of this medical treatment. If the patient has followed the investigator's instructions, Catalyst will pay for reasonable and necessary medical services to treat the injuries caused by the IP or study procedures, if these costs are not covered by health insurance or another third party that usually pays these costs. In some jurisdictions, Catalyst is obligated by law to pay for study-related injuries without prior recourse to third party payer billing. If this is the case, Catalyst will comply with the law.

17 CASE REPORT FORMS AND SOURCE DOCUMENTS

The CRO data management department or designees will perform all data management activities, including the writing of a data management plan outlining the systems and procedures to be used.

Study data will be captured on CRFs and will be verified to the source data, which necessitates access to all original recordings, laboratory reports, and patient records. In addition, all source data should be attributable (signed and dated). The investigator must therefore agree to allow direct access to all source data. Patients must also allow access to their medical records, and patients will be informed of this and will confirm their agreement when giving informed consent. The investigator must review and sign the completed CRF casebook to verify its accuracy.

 Catalyst pharmaceuticals	CMS-001 Version Amendment 5	Page 71
---	--------------------------------	---------

18 STUDY MONITORING AND AUDITING

Qualified individuals approved and/or designated by Catalyst will monitor all aspects of the study according to GCP and SOPs for compliance with applicable government regulations. The investigator agrees to allow these monitors direct access to the clinical supplies, dispensing, and storage areas and to the clinical files, including original medical records, of the study patients, and, if requested, agrees to assist the monitors. The investigator and staff are responsible for being present or available for consultation during routinely scheduled site visits conducted by Catalyst or its designees.

Members of Catalyst's GCP Quality Department or designees may conduct an audit of a clinical site at any time before, during, or after completion of the study. The investigator will be informed if an audit is to take place and advised as to the scope of the audit.

Representatives of the FDA or other regulatory agencies may also conduct an audit of the study. If informed of such an inspection, the investigator should notify Catalyst immediately. The investigator will ensure that the auditors have access to the clinical supplies, study site facilities, original source documentation, and all study files.

19 RETENTION OF RECORDS

The investigator must retain all study records required by Catalyst and by the applicable regulations in a secure and safe facility. The investigator must consult a Catalyst representative before disposal of any study records, and must notify Catalyst of any change in the location, disposition or custody of the study files. The investigator/institution must take measures to prevent accidental or premature destruction of essential documents, that is, documents that individually and collectively permit evaluation of the conduct of a study and the quality of the data produced, including paper copies of study records (e.g. patient charts) as well as any original source documents that are electronic as required by applicable regulatory requirements.

All study records must be retained for at least 2 years after the last approval of a marketing application in an ICH region and until (1) there are no pending or contemplated marketing applications in an ICH region or (2) at least 2 years have elapsed since the formal discontinuation of clinical development of the IP. The investigator/institution should retain patient identifiers for at least 15 years after the completion or discontinuation of the study. Patient files and other source data must be kept for the maximum period of time permitted by the hospital, institution or private practice, but not less than 15 years. These documents should be retained for a longer period, however, if required by the applicable regulatory

 Catalyst pharmaceuticals	CMS-001 Version Amendment 5	Page 72
--	--------------------------------	---------

requirements or by a Catalyst agreement. Catalyst must be notified and will assist with retention should investigator/institution be unable to continue maintenance of patient files for the full 15 years. It is the responsibility of Catalyst to inform the investigator /institution as to when these documents no longer need to be retained.

20 USE OF INFORMATION AND PUBLICATION

Catalyst recognizes the importance of communicating medical study data and therefore encourages their publication in reputable scientific journals and at seminars or conferences. The details of the processes of producing and reviewing reports, manuscripts, and presentations based on the data from this study will be described in the Clinical Trial Agreement between Catalyst and the institution of the investigator.

 Catalyst <small>pharmaceuticals</small>	CMS-001 Version Amendment 5	Page 73
---	--------------------------------	---------

22 INVESTIGATOR RESPONSIBILITIES

22.1 Conduct of Study and Protection of Human Patients

The investigator will ensure that:

- He or she will conduct the study in accordance with the relevant, current protocol and will only make changes in a protocol after notifying the sponsor, except when necessary to protect the safety, rights, or welfare of patients.
- He or she will personally conduct or supervise the study.
- He or she will inform any potential patients, or any persons used as controls, that the drugs are being used for investigational purposes and he or she will ensure that the requirements relating to obtaining informed consent in compliance with ICH E6 (Section 4.8), and other applicable local regulations, are met.
- He or she will report to the sponsor adverse experiences that occur in the course of the investigation in compliance with the standard operating procedures and policies of the IRB/IEC/REB and with applicable regulatory requirements.
- He or she has read and understands the information in the Investigator's Brochure, including potential risks and side effects of the drug.
- His or her staff and all persons who assist in the conduct of the study are informed about their obligations in meeting the above commitments.
- He or she will ensure that adequate and accurate records are kept in accordance with ICH and GCP requirements and to ensure those records are available for inspection.
- He or she will ensure that the IRB/IEC/REB complies with ICH and GCP requirements, and other applicable regulations, and conducts initial and ongoing reviews and approvals of the study. He or she will also ensure that any change in research activity and all problems involving risks to human patients or others are reported to the IRB/IEC/REB. Additionally, he or she will not make any changes in the research without IRB/IEC/REB approval, except where necessary to eliminate apparent immediate hazards to human patients.
- He or she agrees to comply with all other requirements regarding the obligations of clinical investigators and all other pertinent ICH and GCP requirements.
- He or she agrees to comply with electronic signature requirements in accordance with ICH requirements and applicable laws and local regulations.

 Catalyst pharmaceuticals	CMS-001 Version Amendment 5	Page 78
--	--------------------------------	---------

24 APPENDICES

Appendix 1 Subject Global Impression (SGI)

The SGI will be assessed at the protocol-specified time points (see [Table 3](#)) by the patient or the patient's parent/guardian/caregiver if the patient is unable to complete the SGI.

Using the 7-point scale below, rate your impression of the effects of the study medication during the preceding week on your physical well being.

1=Terrible

2= Mostly dissatisfied

3= Mixed

4=Partially satisfied

5= Mostly satisfied

6= Pleased

7= Delighted

Refer to the CMS-001 Study Reference Manual for additional information.

 Catalyst pharmaceuticals	CMS-001 Version Amendment 5	Page 80
--	--------------------------------	---------

Appendix 2 Motor Function Measure (MFM 32 or 20)

The MFM 32 will be used to evaluate the severity and progression of motor function in patients 7 years of age and older. For patients 2 years up to 6 years of age, the MFM 20 will be used to evaluate the severity and progression of motor function. The MFM 32 or 20 (depending on age) will be administered at the protocol specified time points (see [Table 3](#)) by the same well trained evaluator throughout the study.

Each of the 32 items listed below will be graded using a 4-point Likert scale based on the patient's best abilities without any assistance:

- 0 Cannot initiate the task
- 1 Partially performs the task
- 2 Performs the movement incompletely, or completely but imperfectly (compensatory movements, position maintained for an insufficient duration of time, slowness, uncontrolled movement)
- 3 Performs the task fully and “normally”; the movement is controlled, mastered, directed, and performed at constant speed

The 20 motor function measures comprising the MFM20 are marked with ☺ (child <7 years old)

Total score ranges from 0 to 96 when summing the 32 items and from 0 to 60 when summing the 20 items.

Items MFM 32 (from 7 to 60 years)	☺ Items MFM 20 (child <7 years old)	
1. ☺ SUPINE, HEAD IN MIDLINE POSITION: holds the head for 5 seconds in midline position and turns it completely from one side to the other.		
comments :		
2. SUPINE: raises the head and maintains the raised position for 5 second		
comments :		
3. ☺ SUPINE: flexes the hip and knee more than 90° by raising the foot during the whole movement		
comments :		
side :	right : 	left : 
4. ☺ SUPINE, LEG SUPPORTED BY EXAMINER: from the plantar flexion, dorsiflexes the foot to at least 90° in relation to the lower part of the leg.		
comments:		
side :	right : 	left : 
5. ☺ SUPINE: raises the hand and moves it to the opposite shoulder.		
comments:		
side :	right : 	left : 
6. ☺ SUPINE, LOWER LIMBS HALF-FLEXED, KNEECAPS AT THE ZENITH AND FEET RESTING ON THE MAT SLIGHTLY APART: maintains for 5 seconds the starting position then raises the pelvis ; the lumbar spine, the pelvis and the thighs are aligned and the feet slightly apart.		
comments:		
7. ☺ SUPINE: turns over into prone and frees both upper limbs from under the trunk.		
comments:		
side :	right : 	left : 
8. SUPINE: without upper limb support sits up.		
comments:		
9. ☺ SEATED ON THE MAT: without upper limb support, maintains the seated position for 5 seconds and is then capable of maintaining contact 5 seconds between the two hands.		
comments:		

Items MFM 32 (from 7 to 60 years)	⌚ Items MFM 20 (child <7 years old)
10. ☺ Seated on the mat, THE tennis ball placed in front of the PERSON without upper limb support, leans forward, touches the ball and sits back again. comments:	
11. ☺ SEATED ON THE MAT: without upper limb support, stands up. comments:	
12. ☺ STANDING: without upper limb support, sits down on the chair with the feet slightly apart. comments:	
13. SEATED ON THE CHAIR: without upper limb support nor leaning against the back of the chair, maintains the seated position for 5 seconds, with the head and trunk in midline position. comments:	
14. ☺SEATED ON THE CHAIR OR IN THE WHEELCHAIR, HEAD IN FLEXION: from head in complete flexion, raises the head then maintains it raised for 5 seconds, the head stays in midline position throughout the movement and the holding position. comments:	
15. SEATED ON THE CHAIR OR IN THE WHEELCHAIR, FOREARMS ON THE TABLE BUT NOT ELBOWS: places both hands on top of the head at the same time while the head and trunk remain in midline position. comments:	
16. SEATED ON THE CHAIR OR IN THE WHEELCHAIR, THE PENCIL ON THE TABLE: without moving the trunk, reaches the pencil with one hand, forearm and hand off the table with the elbow in full extension at the end of the movement. comments: side : right :  left : 	
17. SEATED ON THE CHAIR OR IN THE WHEELCHAIR, 10 COINS ON THE TABLE: successively picks up and holds 10 coins in one hand during a 20-second period.	

Items MFM 32 (from 7 to 60 years)	☺ Items MFM 20 (child <7 years old)
comments:	
side :	right :  left : 
18. ☺ SEATED ON THE CHAIR OR IN THE WHEELCHAIR, ONE FINGER	
PLACED IN THE CENTER OF THE FIXED CD: goes round the edge of the CD with the same finger without hand support on the table.	
comments:	
side :	right :  left : 
